1 INTRODUCTION

Obstructive Sleep Apnea (OSA) is a condition characterized by the partial or complete collapse of the upper airway during sleep. OSA comprises a continuous spectrum of severity ranging from simple snoring and upper airway resistance through mild to severe symptomatic obstructive hypopnea and apnea. The prevalence of sleep disordered breathing in the adult population is 24% males and 9% for females¹. The prevalence of symptomatic OSA in the adult population has been estimated to be 4% in males and 2% in females¹. These patients demonstrate behavioral and neuropsychological consequences to varying degrees, including excessive daytime sleepiness, intellectual deterioration and depression². More serious consequences include arterial systemic hypertension, arterial pulmonary hypertension and heart disease³.

The treatment of choice for OSA is Positive Airway Pressure (PAP). PAP acts as a positive airway splint, delivering a fixed positive airway pressure to the upper airway via a tube and mask. Humidification is used during PAP therapy to improve comfort of the delivered air and alleviate nasal dryness/congestion.

Although PAP therapy is the gold standard treatment for OSA, adherence to treatment is often poor. CMS guidelines define adherence as 4 or more hours per night of therapy use on 70% of nights during a consecutive 30-day window within the first 90 days of setup⁴. Anywhere from 30 to 85% of patients will be non-adherent according to this definition of adherence, which can be explained, in part, by factors such as socioeconomic status, age, gender, severity of presenting symptoms, health values/beliefs, and social support⁵. Importantly, patients who immediately adopt therapy, within the first 3 days, are significantly more likely to be adherent at 30 days⁶, and patients' usage at 1 month is significantly predictive of adherence at 1 year⁷. Without sustained, long-term therapy adherence, patients are at risk of negative health outcomes including but not limited to cardiovascular disease, stroke, diabetes, and depression. This study tests whether a combined financial plus social incentive can help users new become adherent to PAP therapy.

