3.2 STUDY DESIGN

This is a prospective, randomized, two-arm, open-label study to evaluate effectiveness of applying financial and social incentives via a smartphone-based app in helping participants achieve adherence to therapy. Randomization will include an allocation ratio of 2:1 (control:treatment).

Two 'site to participant' contacts are required during this study. These contacts can either occur at the clinical site or remotely (e.g., by telephone). During the initial contact, their interest in the study and eligibility will be confirmed, then they will be consented, asked to complete the Baseline Questionnaire, and their demographic information will be collected on case report forms (CRFs).

Participants randomized to the intervention (Group B) will be provided with information and assistance in downloading Restful to their smartphone and registering with Wellth.

At the final contact (90 days), the participant will be asked to complete an End of Study Questionnaire and the investigative staff will collect PAP therapy data for the trial period and record it on CRFs. Participants in Group B will have access to the Restful app discontinued. This completes the participant's active participation in the study.

Daily usage data from AirView will be collected and transmitted electronically from usage initiation to 90 days, and then through 180 days.

Study data will be captured on CRFs. See **Appendix A** for the **Baseline and End of Study Questionnaires**. See **Appendix B** for **Participant Instructions** related to the study procedures and the Restful app.

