3.7 STUDY ENDPOINTS

Primary Endpoint: mean PAP usage at 90 days collected from participants' flow generators

Secondary Endpoints:

- Percentage of participants that meet the Medicare compliance standard (at least 4 hours per day on at least 70% of the days in a consecutive 30-day period any time in the first 90 days of therapy)
- Change in ESS and FOSQ-10 questionnaire scores
- Baseline scores of perceived disease severity, claustrophobia, coping skills, and health literacy as moderators of the intervention's effectiveness

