3.9 DATA ANALYSIS

Baseline demographic and psychosocial factors will be summarized for each randomized group for ITT and Evaluable Populations. For continuous variables, such as age and PAP usage, the mean, standard deviation, median, and range will be presented. For categorical variables, such as gender, the number and proportion of participants in each category will be presented. Baseline demographics and psychosocial factors for the control and intervention groups will be compared with t-tests and Fisher's exact tests, as appropriate.

The primary analysis compares mean PAP usage at 90 days in the control and intervention groups using a two-way ANOVA on the ITT population. Randomization group and myAir usage (Yes/No) will be included as factors in the model. The interaction of the two factors will be considered, but will only be retained in the model if it is significant at the 5% level. Missing usage hours during a day will be imputed as 0 usage. A secondary analysis of mean PAP usage will be conducted using the Evaluable Population. A sensitivity analysis of the missing data assumption will be conducted by considering missing data as missing. In this analysis, participants with no usage data will be assumed to have a mean usage of 0 hours; other participants' mean usage will be calculated as the mean usage across nights for which there is data.

A subgroup analysis of the primary endpoint will be generated for patients who are identified as strugglers. A struggler is defined as a patient who uses their device for less than or equal to 3.5 hours/night during the first 3 days of usage. Mean PAP usage at 90 days will be compared in the control and intervention groups using a two-way ANOVA on the struggler population as described above. Descriptive statistics will also be presented for mean PAP usage, comparing strugglers and non-strugglers in control and intervention groups.

Adherence will be calculated for the ITT population from daily usage data using the Medicare definition for adherence (a patient is adherent if they use the device for more than 4 hours per night for 70% of the nights during the first 90 days of usage). Percent adherence will be compared between control and intervention groups using a logistic regression model on the ITT population. Randomization group, myAir usage, and the interaction of these two factors will be included in the model. Missing usage hours during a day will be imputed as 0 usage.

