5 INTERVENTION

5.1 WELLTH APP (RESTFUL)

The intervention is the use of Restful, the Wellth self-management application. There is no clinical treatment intervention, as all participants will be receiving PAP therapy per standard of care.

Restful is a smartphone-based patient engagement tool that utilizes concepts from behavioral economics to help patients improve their adherence to therapy. The intervention includes:

Financial incentive:

The incentive is \$75, and is distributed as follows: Participants unlock \$5 after completing the app introduction/onboarding, and then \$10 for successful nights on days 1, 2, 3, 5, 8, 13, and 21. Successful nights are nights where therapy is used for ≥ 4 hours. Once money is "unlocked," the reward is always visible to the participant. However, participants only receive the financial reward if they unlock all \$75 by the end of the program. In between

“pay days,” participants receive positive reinforcement messages and visual cues but no financial reward is unlocked.

Recognizing that participants are likely to struggle initially, and that there are 9 days in which participants can afford to have non-adherent nights (i.e., $30 - 21 = 9$), the participants will be granted 9 hearts in the app. These hearts represent the “misses” available to them, and they will lose a heart each non-adherent night. The program will deliver a tailored intervention message of support or encouragement after every 2 lost hearts (e.g., remind participants how close they were to a successful night).

If the participant does not meet adherence in the first 5 weeks and/or they have lost 9 hearts, then they will get a second chance. The intervention will “reboot.” Participants will not be made aware of this opportunity at the outset.

Social incentive:

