The social incentive will have two components: social currency and social support messages. Participants will have the opportunity to nominate a social support person during the Wellth onboarding process. This person will be contacted directly by Wellth via text message and provided with information that will explain their role in supporting the participant. The support person will be asked to provide social currency (described below) that they think will be meaningful to the participant, as well as some supportive messages. Over the course of the 90-day trial, Wellth will reach out to the support person to solicit additional currency and messages. If the support person is generally non-responsive, or if the participant does not nominate a social support person, then the participant will receive Wellth-designed content for the social currency and social support components.

- Social currency: Pictures and/or videos that are meaningful to the participant. Delivered to the participant when they hit a therapy usage streak of 3 days in a row ≥ 4 hours.
- Social support messages: Encouraging messages that are meaningful to the participant. Delivered to the participant at seemingly random intervals throughout the 90 days (i.e., via a rules-based delivery algorithm).

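### Medicare adherence is defined as 21 of any 30 consecutive days in section 3.7 but as 63 of 90 nights in section 3.9; on a common day 1, the section 3.9 rule understates each arm's rate

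*Combined protocol and SAP*

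**What the plan says.** Section 3.7 counts a participant as compliant with "at least 4 hours per day on at least 70% of the days in a consecutive 30-day period any time in the first 90 days". The Introduction describes the CMS rule in the same way, with 4 or more hours on 70% of nights "during a consecutive 30-day window within the first 90 days of setup".

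Section 3.9 is the only place that says how the endpoint is computed. It states: "Adherence will be calculated for the ITT population from daily usage data using the Medicare definition for adherence". It then spells that definition out as "more than 4 hours per night for 70% of the nights during the first 90 days of usage", with no 30-day window. Days without usage data count as 0 hours, and the arms are compared by logistic regression in the ITT population.

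The app in section 5.1 is built on the 30-day rule: 21 successful nights, 9 permitted misses, and success at 4 hours or more.

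**The concern.** The two rules share a label and a percentage but define different endpoints. The main difference is the window: the best 30 consecutive days against all 90. There are two smaller mismatches. The hour threshold is at least 4 in section 3.7 and more than 4 in section 3.9. Day 1 is setup in the Introduction, therapy in 3.7 and usage in 3.9.

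An analyst who follows 3.9 literally will report, as Medicare adherence, a rate that is not the stated endpoint and is probably well below it. The trial is open-label and the same daily data serve both rules. Leaving both in the plan therefore allows the choice to be made after the results are known. The choice can also change the arm comparison, because the app's financial incentive is tied to 21 of 30 nights.

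**Working it through.** **Plan's own figure.** The documents give no rate, effect or power for adherence. The only sample-size figure is for mean usage (section 3.6: difference 0.8 h, SDs 2.5 and 2.0, one-sided 0.025, 180:90). The standardised difference is 0.8 / √(2.5²/180 + 2.0²/90) = 0.8 / 0.281 = 2.84. The unequal-variance t-test then has 80.8% power, and the smallest 2:1 design reaching 80% is 178:89 = 267. The stated 270 reproduces, and 270/0.9 = 300. None of this depends on the adherence definition.

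**Thresholds.**
- Section 3.7: 0.70 × 30 = 21 days in some 30-day run, so 9 misses are allowed in the best 30.
- Section 3.9: 0.70 × 90 = 63 nights, so 27 misses are allowed in 90.

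**Nesting on a common day 1.** Split 90 nights into three blocks of 30. With 63 successes, at least one block holds 63/3 = 21 or more, so 3.9 adherence implies 3.7 adherence. The stricter hour threshold in 3.9 works in the same direction. The converse fails: 30 of 30 nights followed by 20 of 60 meets 3.7, but 50/90 = 56% fails 3.9.

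**If the clocks differ.** With every 30-night window held to 20 successes, the most possible in 90 nights is 3 × 20 = 60. If the usage clock starts g nights after setup, it also counts g later nights that no 3.7 window covers. The maximum is then 61 for a gap of 1 night, 63 for 3 nights and 67 for 7 nights. Nesting can therefore fail from a 3-night gap.

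**Participants given a second chance.** Section 5.1 restarts the app for someone who "does not meet adherence in the first 5 weeks and/or they have lost 9 hearts". Assume that missing adherence means at most 20 successes in 35 nights. Such a participant can still reach 21 of 30 later and meet 3.7. Under 3.9 they need 63 − 20 = 43 of the remaining 55 nights (78%). With 7 or fewer early successes, 7 + 55 = 62 < 63, so 3.9 is out of reach.

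**Constant nightly probability p, independent nights (illustration).**

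| p | 3.7 | 3.9 |
|---|---|---|
| 0.50 | 18.5% | 0.01% |
| 0.60 | 70.8% | 3.2% |
| 0.70 | 98.6% | 55.2% |
| 0.80 | >99.9% | 99.2% |

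**Varied patients (all inputs assumed).** Nightly success logit = intercept (−0.5, 0, 0.4) + patient effect (SD 1.5 or 2) + random linear slope over 90 nights (SD 1, 2 or 3), with the slope anchored at night 1 or mid-period. That gives 3 × 2 × 3 × 2 = 36 settings, with 40,000 patients per arm in each. Control-arm adherence is 34-65% under 3.7 and 17-42% under 3.9, a gap of 11-29 points. For a benefit of +1 on the logit scale, the arm differences in percentage points are:

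| Benefit lasts | 3.7 | 3.9 |
|---|---|---|
| Nights 1-30 only | 9-14 | 4-8 |
| Nights 1-35 only | 9-16 | 5-9 |
| Half the effect after night 30 | 12-19 | 10-17 |
| All 90 nights | 15-26 | 15-26 |

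Re-runs move these limits by about a point. In the last row, which rule gives the larger difference varies by setting and by run, so the two should be read as equal.

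**A second model.** Using section 3.6's between-patient SDs with assumed means of 3.5-5.8 h and night-to-night SDs of 1.5-2.5 h, the gap is 8-17 points. It is 10-20 points if 20% stop use on a random day.

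**The case against.** The strongest reply is that the parenthesis in 3.9 is loose shorthand. The sentence invokes the Medicare definition, which the protocol gives consistently twice elsewhere, and a careful analyst might apply that version. This is possible, but the parenthesis is a complete rule in the analysis section. The objectives also speak of adherence at 90 days, which makes a whole-period reading plausible. The text does not settle the matter.

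A second reply is that this is an unpowered secondary endpoint with no stated hierarchy, and that the bias in the arm difference has no known direction. That stands. The app's restart, and social messages "Delivered to the participant at seemingly random intervals throughout the 90 days", make a longer benefit plausible, so dilution under 3.9 is a possibility and not a prediction. It does not rescue the reported rates, which would still carry the wrong label.

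Third, the size rests on chosen inputs. The gap is 11-17 points at slope SD 1, 14-23 at SD 2 and 15-29 at SD 3; with no slope it is 10-15. The upper end should carry little weight.

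Finally, some of the detail is minor. The hour threshold matters only for nights of exactly 4 hours. The second-chance arithmetic covers one of two triggers, since losing 9 hearts can restart the app well before night 35.

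**Conclusion.** The concern holds. As written, the first-listed secondary endpoint has two different definitions, and the section that governs its analysis states the one that does not match the endpoint. On a common day 1 the 3.9 rate can never exceed the 3.7 rate. It is lower in any arm with at least one participant who has a qualifying 30-day run but fewer than 63 qualifying nights. That direction is exact given the common start; the size is illustrative, at roughly 8-29 points across the two assumed models. No direction is claimed for the difference between arms. The primary comparison of mean usage and the sample size of 300 are untouched. The contradiction should be removed before the data are analysed.

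**What to change.** Replace the parenthesis in section 3.9 with the section 3.7 rule: a participant is adherent if any run of 30 consecutive days within the first 90 contains at least 21 days with at least 4 hours of use. State one day 1 for the 90-day period and use it in the Introduction, 3.7 and 3.9. If use across the whole 90 days is also of interest, report the 63-of-90 measure separately as sustained 90-day adherence, without the Medicare label. This also answers the fair criticism that the 3.7 rule credits someone who was adherent in only one 30-day window.

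The cost is a one-sentence amendment, a stated start day and a rolling 30-day count in the analysis program. No new data are needed, since section 3.2 already provides that "Daily usage data from AirView will be collected and transmitted electronically from usage initiation to 90 days".

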3.6 SAMPLE SIZE

N= 300

A minimum total sample size of 270 patients, with 2:1 randomization (180 in Control group, 90 in Test group) is required to yield an 80% probability of detecting a difference of 0.8 hours in mean usage (160% of the minimally clinically significant difference) when the standard deviation is 2.5 and 2.0 in the Control and Test groups, respectively. The required sample size was calculated in the Two Sample T-Tests Assuming Unequal Variances Procedure using NCSS Power Analysis Statistical Software, Version 16 (PASS 16¹⁴) based on a one-sided, two sample t-test, using a significance level of 0.025.

Assuming a potential 10% drop-out rate due to study withdrawal or lost-to-follow-up, the final sample size will be 300 patients (270/0.9), equating to 200 in the Control group and 100 in the Test Group. The 2:1 randomization ratio was chosen because it is more cost-effective to enroll subjects in the control group.

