5.3 MYAIR

In addition to AirView, a patient-focused version of the data is available through the myAir app. The myAir app can be accessed via the participant's smartphone or computer and allows the participant to monitor their own treatment data. myAir also provides tips to the participant on things like coping with therapy, managing mask leaks, and adjusting comfort settings. These tips are personalized based on each individual's data. The myAir app is not mandatory in this trial, but participants' usage of myAir will be documented in both Group A and Group B.

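### The adherence logistic model always contains the group-by-myAir interaction but names no coding or contrast, so the overall between-arm adherence effect is undefined

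*Combined protocol and SAP*

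**What the plan says.** Section 3.7 lists adherence first among the secondary endpoints: "Percentage of participants that meet the Medicare compliance standard". Section 3.9 gives the purpose and method: "Percent adherence will be compared between control and intervention groups using a logistic regression model on the ITT population". The model terms follow: "Randomization group, myAir usage, and the interaction of these two factors will be included in the model". No condition is attached to the interaction.

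For the primary ANOVA on mean usage, the same section says "Randomization group and myAir usage (Yes/No) will be included as factors in the model", and there the interaction "will only be retained in the model if it is significant at the 5% level".

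On myAir itself, Section 5.3 says: "The myAir app is not mandatory in this trial, but participants' usage of myAir will be documented in both Group A and Group B". Section 4.4 describes a report, produced at 90 and 180 days, of who registered for myAir and how often they engaged with it during the study. The plan does not say at what time, or by what rule, a patient counts as a myAir user.

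The plan nowhere states how group and myAir are coded, which myAir level is the reference, or which coefficient, contrast or standardised difference answers the between-arm question.

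**The concern.** Once a product term is in a logistic model, the group coefficient is no longer an overall effect, and its meaning depends on how the factors are coded. The protocol promises a comparison of percent adherence between arms, then specifies a model that can produce several different group effects and does not choose among them. The choice would fall to whoever writes the program, possibly by software default and possibly after the data are seen.

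Two things are at stake for this endpoint. The reported group effect could differ widely from the difference between the randomized arms if the effect varies with myAir use. If it does not vary, the group test could still have much less power than the sample allows.

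A further point bears on interpretation. myAir use is optional and appears to be recorded during follow-up, so the strata may be formed after randomization and may themselves be affected by the intervention.

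**Working it through.** **1. The plan's own figure.** Section 3.6 sizes the trial on mean usage: "A minimum total sample size of 270 patients, with 2:1 randomization (180 in Control group, 90 in Test group"), for an "80% probability of detecting a difference of 0.8 hours in mean usage", with SDs of 2.5 and 2.0 and one-sided alpha 0.025. SE = √(2.5²/180 + 2.0²/90) = √(0.0347 + 0.0444) = 0.281, and 0.8/0.281 = 2.84. Power is Φ(2.84 − 1.96) = 81.1% by the normal approximation and 80.8% with the noncentral t. 270/0.9 = 300. The stated size reproduces. The documents give no power, adherence rates or myAir share for the adherence endpoint, so everything below rests on assumed values.

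**2. What the group term estimates.** Let L0 and L1 be the log odds ratios for group among myAir non-users and users.
- Reference coding, non-users as reference: the group coefficient is L0. With users as reference it is L1.
- Effect coding (±1): twice the group coefficient is (L0 + L1)/2, whatever the share of users.
- Arm level: the log odds ratio of the two overall percentages, which depends on the share of users.

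Illustration, with assumed control adherence of 50% (non-users) and 65% (users), and the same myAir share in both arms:

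| Test arm, non-users / users | myAir share | L0 | L1 | Equal-weight average | Arm percentages | Arm-level log OR |
|---|---|---|---|---|---|---|
| 50% / 80% | 50% | 0.000 | 0.767 | 0.384 | 57.5% v 65.0% | 0.317 |
| 50% / 80% | 30% | 0.000 | 0.767 | 0.384 | 54.5% v 59.0% | 0.183 |
| 70% / 65% | 50% | 0.847 | 0.000 | 0.424 | 57.5% v 67.5% | 0.429 |

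With non-users as reference, the coefficient is zero in the first row although the arms differ, and about twice the arm-level value in the third (0.847 v 0.429). The equal-weight average is close in the third row but about double in the second (0.384 v 0.183).

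**3. Power when there is no interaction.** Assumptions: overall adherence 55% v 72%, 200 control and 100 test patients, myAir log-odds 0.7, equal myAir share in both arms, two-sided 5% Wald test.

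At a 50% share, solving for the arm percentages gives control rates of 46.4% (non-users) and 63.6% (users), test rates of 65.1% and 78.9%, and a common log odds ratio of 0.765. Each cell contributes 1/[n·p·(1 − p)] to the variance:
- Non-users: 1/(100 × 0.464 × 0.536) + 1/(50 × 0.651 × 0.349) = 0.128, SE 0.358.
- Users: 1/(100 × 0.636 × 0.364) + 1/(50 × 0.789 × 0.211) = 0.163, SE 0.404.
- Equal-weight average: √[(0.128 + 0.163)/4] = 0.270.
- No interaction: √[1/(1/0.128 + 1/0.163)] = 0.268.

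Power is Φ(0.765/SE − 1.96). The same steps at the other shares give:

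| Group test | 30% use myAir | 50% | 70% |
|---|---|---|---|
| Interaction model, non-users as reference | 70% | 57% | 39% |
| Interaction model, users as reference | 29% | 47% | 64% |
| Interaction model, effect coding | 69% | 81% | 77% |
| Interaction model, contrast weighted by myAir share | 81% | 81% | 81% |
| No interaction | 81% | 81% | 81% |

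A simulation of 1,500 trials per setting with non-users as reference agrees: 68%, 57% and 37% with the interaction, 81% to 82% without.

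**4. Cost of leaving myAir out.** For 55% v 72% unadjusted, the log odds ratio is 0.744 and SE = √[1/(200 × 0.55 × 0.45) + 1/(100 × 0.72 × 0.28)] = √(0.0202 + 0.0496) = 0.264. Power is Φ(0.744/0.264 − 1.96) ≈ 80%, against 81% with myAir in the model.

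**The case against.** A reader might infer that the group coefficient is always a one-stratum effect, that no arm comparison can be had from this model, or that including the interaction itself costs power. The documents support none of these. The one-stratum reading needs reference coding, which Section 3.9 does not specify. The stated aim is a between-arm comparison, and a share-weighted contrast or standardised arm percentages could be taken from the same fit. The last two rows of the power table show almost no loss once a suitable contrast is used. The fall to 39% at a 70% share, or to 29% at a 30% share with users as reference, belongs to particular coding choices.

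Nor is it an error that the primary ANOVA treats the interaction differently. Different endpoints may have different models, and always including a term at least avoids choosing the model from the data.

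It would also go too far to say that the myAir strata are certainly formed after randomization. Sections 4.4 and 5.3 point that way, but the plan does not define when use is determined. The same question arises for the primary ANOVA and does not depend on the interaction.

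All of this stands, and it narrows the point. It does not remove it: an arm comparison could be obtained from the model, but the plan does not say which one.

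**Conclusion.** The point holds as a gap in specification. The adherence analysis has a stated purpose and a stated model, but no defined estimate linking them, and the usual group coefficient is not in general the arm-level comparison.

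The algebra in step 2 does not depend on the assumed rates. The sizes do: adherence rates, the myAir share, its association with adherence and its equality between arms are all assumptions. Within them, the unstated coding alone moves power between about 29% and 81%. Adherence is a secondary endpoint and the trial is sized on mean usage, so the sample size is unaffected. This is a cheap improvement worth making before the data are analysed.

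**What to change.** In Section 3.9, make the main adherence comparison a logistic model on the ITT population with randomized group and only covariates fixed before randomization, without the interaction. Report the overall odds ratio and the risk difference with confidence intervals. Put myAir use and group-by-myAir in a separate model labelled exploratory, and state its factor coding and how and when myAir use is determined.

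If the planned model is kept as well, state that its arm comparison is the standardised difference in percent adherence and not the group coefficient.

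The cost is about one sentence and no new data. The downside is that the main adherence model no longer adjusts for myAir use. Under the assumptions above that is worth about one percentage point of power.

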3.8 ANALYSIS POPULATIONS

Randomized Population: all participants enrolled and randomized to treatment groups.

Intent-to-Treat (ITT) Population: all participants randomized to control or intervention group, regardless of the actual intervention received.

Evaluable Population: all ITT subjects who complete the 90-day study period and complete the end-of-study questionnaire.

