Mean change in ESS and FOSQ questionnaire scales will be compared between control and intervention groups using a mixed-effects linear model on the ITT population and a two-sample t-test on the Evaluable population. In the mixed-effects model, the response variable will be the mean questionnaire score and the model will include randomized group, visit, and a randomized group by visit interaction as fixed effects and subject as a random effect.

Baseline perceived disease severity, claustrophobia, coping skills, and health literacy will be tested as moderators of the intervention's effectiveness. Baseline scores will be regressed on the primary outcome (usage), and then in a mixed-effects model, the response variable will be usage and the model will include baseline score, randomized group, and a randomized group by baseline score interaction as fixed effects and subject as a random effect.

An exploratory analysis will examine how engagement with the study is associated with PAP usage. Engagement will be measured as app usage (number of touches). A linear regression model with PAP usage as the dependent variable and engagement as the independent variable will be fit to all ITT subjects (engagement is zero for all control subjects). An exploratory analysis will also test whether the intervention has a direct or indirect effect on the following psychosocial factors: the pros and cons of change, self-efficacy, and social support. Finally, an exploratory analysis will test whether nomination of, and the extent of engagement with, a social support person moderates the intervention effectiveness.

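### Both planned ESS/FOSQ analyses learn day-90 change only from participants who return the form, and neither uses the device-recorded usage that could relax that assumption

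*Combined protocol and SAP*

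**What the plan says.** Section 3.9 compares mean change in ESS and FOSQ between arms "using a mixed-effects linear model on the ITT population and a two-sample t-test on the Evaluable population". The mixed model has group, visit and their interaction as fixed effects and subject as a random effect. It has no usage term. No missing-data rule and no sensitivity analysis is given for these scores.

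The Protocol Summary and sections 4.2 and 4.3 place the questionnaires at baseline and about 90 days later, with nothing between. Section 3.8 defines the Evaluable Population as "all ITT subjects who complete the 90-day study period and complete the end-of-study questionnaire".

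Usage reaches the statistician by another route. Section 3.2 states: "Daily usage data from AirView will be collected and transmitted electronically from usage initiation to 90 days". Section 5.2 says the device transmits after each period of use, and section 4.4 has a central group produce the usage report at 90 and 180 days. None of this depends on the day-90 form.

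For usage itself, section 3.9 does give a rule, "Missing usage hours during a day will be imputed as 0 usage", and a sensitivity analysis that treats missing nights as missing.

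**The concern.** With two visits, a participant without the day-90 form contributes one baseline score. Likelihood estimation then implies for that person the change expected of same-arm responders with the same baseline score. This is valid only if, given arm and baseline, returning the form is unrelated to the day-90 score.

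That is doubtful here. Someone who has largely given up PAP may be less likely to complete the form and less likely to have improved. The Evaluable t-test cannot reveal the problem, because it too learns about change only from people who returned the form.

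At stake is the arm comparison on a secondary endpoint. The intervention is meant to raise usage. If it succeeds and non-response follows low usage, non-response will differ between arms and the two arms will be distorted by different amounts.

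**Working it through.** **1. The plan's own figure.** Section 3.6 claims an "80% probability of detecting a difference of 0.8 hours in mean usage", "when the standard deviation is 2.5 and 2.0 in the Control and Test groups, respectively", "based on a one-sided, two sample t-test", "using a significance level of 0.025". With 180 and 90 participants:

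- SE = √(2.5²/180 + 2.0²/90) = √(0.0347 + 0.0444) = 0.281
- 0.8/0.281 = 2.84, with about 217 Welch degrees of freedom
- Power = 80.8%. The smallest 2:1 design reaching 80% is 178 + 89 = 267.
- 270/0.9 = 300

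The sample size reproduces, and this point does not touch it. No corresponding figure exists for ESS or FOSQ.

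**2. Inputs for the ESS check.** From section 3.6: usage SDs 2.5 h (control) and 2.0 h (test), a 0.8 h difference, 2:1 allocation and 10% drop-out, used here as the overall non-response share. Assumed, not in the documents:

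- mean usage 4.0 h and 4.8 h, truncated at zero, which gives 4.06 h and 4.81 h, a difference of 0.747 h
- ESS lower by β = 0.4 to 0.8 points per hour of use
- log-odds of non-response lower by 0.5 to 1.0 per hour of use
- baseline score unrelated to usage

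**3. Formula.** Under these assumptions the planned model overstates an arm's improvement by

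β × (mean usage of responders − mean usage of the whole arm).

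The bias in the arm difference is β times the gap between the two arms' shifts. Numerical integration gives:

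| Overall non-response; log-odds per hour | Non-response, control / test | Shift, control / test (h) | Gap (h) |
|---|---|---|---|
| 10%; 0.5 | 11.3% / 7.4% | 0.252 / 0.132 | 0.120 |
| 10%; 1.0 | 12.2% / 5.6% | 0.397 / 0.165 | 0.232 |
| 20%; 1.0 | 23.4% / 13.1% | 0.750 / 0.356 | 0.394 |

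**4. Results (negative favours the app).** The true difference is −β × 0.747.

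- Mildest (10%, 0.5, β = 0.4): true −0.299; bias 0.4 × 0.120 = 0.048; planned model −0.251. Loss 16%.
- Strongest at 10% (1.0, β = 0.8): true −0.598; bias 0.8 × 0.232 = 0.185; planned model −0.412. Loss 31%.
- 20% (1.0, β = 0.6): true −0.448; bias 0.6 × 0.394 = 0.236; planned model −0.212. Loss 53%.

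Individual simulation runs scatter around these values: at 10%, from −0.26 against −0.30 (13% lost) to −0.39 against −0.58 (33% lost). In those runs the completers' comparison was within 0.01 of the likelihood estimate, and conditioning on usage recovered the true difference. A fitted random-intercept model with 18.6% and 9.9% non-response gave −0.26 against a true −0.44.

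**5. When the bias vanishes or changes sign.**

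- If usage has the same distribution in both arms, the shifts are equal and the bias in the difference is zero.
- In a simpler model, non-responders do not improve at all. With 10% non-response in both arms and a responder difference of 1.0, the true difference is 0.9 × 1.0 = 0.90, so the planned model overstates by 0.10.
- In the same model with 15% control and 5% test non-response and equal responder improvement of 3 points, the true difference is 0.95 × 3 − 0.85 × 3 = 0.30, which the planned model reports as 0.

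**The case against.** A reader might infer that section 3.9 contradicts itself, by assuming 0 h for a drop-out in the usage analysis and a responder's improvement for the same person in the ESS model. The documents do not support that. The zero rule covers days without device data, not people who skip the form. A participant who ignores the day-90 contact while the device still transmits keeps measured hours. The two assumptions pull apart only where device data are absent, and different outcomes may reasonably have different missing-data rules.

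A reader might also infer that the plan is tilted towards showing a benefit. That is not supported either. Overstatement within each arm largely cancels when non-response is balanced, and where non-response follows usage the difference was attenuated.

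Large imbalances cannot be taken for granted. At 10% overall and 2:1 allocation, control non-response 20 points above test would need 16.7% and −3.3%, which is impossible. The reverse would need 23.3% in test and 3.3% in control, and nothing in the documents suggests it. Both arms are asked for the forms, and compensation is distributed at that contact.

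The mixed model on ITT is a conventional choice. Imputation from usage is itself a missing-at-random method, and device data may be lacking for participants who withdraw or revoke authorization (section 6.1). These objections stand. They make this an improvement rather than the correction of an error, and they shape the fix. They do not remove the point that both planned analyses share one untested assumption while a relevant variable goes unused.

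**Conclusion.** The point holds as an inexpensive improvement to secondary endpoints. The primary endpoint and the sample size are unaffected.

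With non-response near the planned 10%, driven by usage, and a true benefit, the planned ESS difference is attenuated by about 0.05 to 0.19 points (0.04 to 0.19 across simulation runs). It is larger if more forms are missing, and small if non-response is balanced and the arms do not differ. The direction is not fixed; it depends on how non-response relates to arm and usage.

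The sizes rest on the assumed ESS slope, usage means and non-response relation. The documents give no ESS or FOSQ effect size, SD or threshold, so clinical materiality cannot be judged from them. FOSQ-10 was not sized.

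**What to change.** In section 3.9, add a prespecified ITT analysis of ESS and FOSQ-10:

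- Multiply impute missing day-90 scores by arm from the baseline score and device usage (mean hours over 90 days and over the last 30 days), then compare arms.
- Keep usage in the imputation model only. It is measured after randomization and lies on the pathway of the intervention, so it must not be a covariate in the comparison.
- State how participants without device data are handled, for example by imputing their usage jointly with the score and repeating with 0 h.
- Add a sensitivity analysis in which non-responders whose device data show that PAP stopped are given their baseline score, with the definition of stopped fixed in advance for this analysis.
- Report day-90 questionnaire completion by arm.

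The planned mixed model can stay. The cost is SAP wording and a little more programming, with no new contacts or data collection. The limitation is that imputation in the smaller arm (100 participants, about 6 or 7 missing scores in the 10% scenarios above) relies on few low-use responders.
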